1.2	12AUG2016	Non-Substantial Amendment 02	
Version control and date updated throughout the document.Changes to the group orders to harmonise with study schematic figure on page 48, at pages 32, 48, 56.Addition of Principal Investigator approval section for [name] as PI at the HMR Pharmacy Site.Section 1: Addition of PI details for [name].Section 7.3: Exclusion Criteria:
1) Amendment to the smoking criteria2) Amendment to BMI criteria3) Amendment to the reference to vulnerable populations4) Amendment to criteria to prevent duplicationSection 9: Clarification on the conditions for end of Quarantine phase.Table 9-2: Removal of LDH and Uric Acid from the Biochemistry panel as reflected in the Time & Events (T&E) schedule and throughout the protocol, as it does not add significant safety information in a healthy & young population.Table 9-2: Removal of Biochemistry from Day 5 assessments as it does not add significant safety information.Table 9-2: Clarification on the conduct of the safety blood analysis on the Follow-Ups (Day 35 and 63) will be conducted at PIs discretion.Keynotes for T&E Schedule:
1) Clarifying the conduct of the FLU-PRO to be in line with the Protocol text.2) #7: Clarifies that a viral challenge serology test may be repeated if required, if subjects fall out of the 90-day window. Additionally, clarifying that the screening

DETAILS OF AMENDMENTS			
			
visit includes collection of PBMC and PAXgene from subjects invited to receive IMP before their vaccination visit.
 
 Section 10 & 13: Clarification that HMR SOPs will be followed when appropriate. Section 13.2.3: Clarification that no protocol deviation will be recorded due to missing diary card data. Furthermore, the diary card data will be reviewed by a physician in retrospect and complete the information as accurately as possible by asking the subject about symptoms for the missing data sets. Grammatical and formatting changes have been made throughout the document.
1.3	26Aug2016	Non-Substantial Amendment 03	
 Section 5.3, page 32 - updated the order of group numbering Section 9, page 47, updated the order of group numbering and removed the Figure 1 Section 10, page 56, updated the order of group numbering Exclusion criteria 1 - clarified exclusion criteria 1
2.0	26SEP2016	Substantial Amendment 01	
 Section 7.2; Inclusion Criteria 9: Clarification to participant asthma history prior to entry into study. Section 7.2; Inclusion Criteria 11: Clarification on the time-point for acquiring a subject's medical history from their GP. Section 18.7.1; Informed consent procedure: Amended to include Investigator or delegate to conduct participant consenting. Section 18.7.3; Information for General Practitioners: Amendment to the requirement for participant's medical history from their GP.
2.1	09DEC2016	Non-Substantial Amendment 04	
 Protocol has been clarified throughout to allow variable entry to the Quarantine unit on Day -2 or Day -1. The changes are further reflected in the study design, Time & Events schedule and individual assessments where appropriate. Sections 7.2 & 18.7.1: Clarification on the responsibilities of the Investigator or delegate in the consenting process for participants. Keynotes to the Time & Events schedule & Section 14.1.3: Clarification on the collection of pre-vaccination PAXGene and PBMC samples in the Time & Events schedule.

DETAILS OF AMENDMENTS			
			
Section 18.7.3: Clarification on the confirmation of volunteers' medical history from their medical practitioner.
2.2	31JAN2017	Non-Substantial Amendment 05	
Correction of Section 7.2; Inclusion Criteria 9: Participant asthma history prior to entry into study to match the wording included in the MHRA and Research Ethics Committee -approved version 2.0 of the study protocol, which was incorrectly reverted to the original wording in protocol version 2.1.
3.0	18APR2017	Substantial Amendment 02	
Pages 1, 6 and 12 updated to reflect change in PI.Section 6.3.1 and throughout updated to reflect exploratory endpoints may be reported separately from CSR.Section 9.3.1 correction for consistency that subjects will be admitted to the Quarantine unit with a minimum 20 days not 21 days post second vaccination.Section 9.3.1 and throughout a clarification that serology test and result must be available within 90 days of Day 0 inoculationSection 13.1.2 inspection of the eyes removed from mandatory list in directed physical examination.Section 13.2.2 language inserted to state how missing Flu-PRO data will be handled.

SPONSOR'S AUTHORISATION

[figure not shown]

2 PROTOCOL SYNOPSIS

SYNOPSIS	
TITLE	Phase IIb Study of the Efficacy of FLU-v, a Broad Spectrum Influenza Vaccine in an H1N1 Influenza Healthy Human Challenge Model
SPONSOR	PepTcell Limited (t/a SEEK)
SPONSOR PROTOCOL NO.	FLU-v-004
PHASE	Phase IIb
INDICATION	Prophylaxis of Influenza
EUDRACT NUMBER	2016-002134-74
STUDY DESIGN	
A randomized, double-blind, placebo-controlled efficacy and safety trial of FLU-v administered as 2 vaccinations or 1 vaccination vs placebo prior to intranasal challenge with the Influenza A 2009 H1N1 human virus.
 
In this study, the main efficacy comparisons are for each of the FLU-v groups to placebo. The study will also compare the two FLU-v dosing arms but will only have power to detect a significant difference in Mild to Moderate Influenza Disease (MMID) rates between the FLU-v groups and placebo and not against each other.
 
Assuming significant efficacy of at least one dose of FLU-v against placebo is demonstrated in the current protocol (Part A), when the primary efficacy endpoint and key safety results are available, the protocol may be amended to include a second part (Part B) which will test the optimal FLU-v dose from Part A (in terms of efficacy and safety) versus current standard of care seasonal influenza vaccine. Details of Part B will be determined and documented in a future protocol amendment following the availability of the unblinded key efficacy and safety results from Part A. Approval will be sought via a substantial amendment from the competent authority before part B can commence.

SAMPLE SIZE	Up to 123 participants inoculated with the challenge virus
RANDOMISATION AND BLINDING	
Randomisation will occur on day -43.
 
Part A
 
FLU-v 1 or 2 doses and placebo treatment arms will be double-blinded and randomised 1:1:1.

SYNOPSIS	
	
Randomisation numbers will follow a 3 digit format e.g., 101-1NN. A copy of the randomisation code list will be sent to the unblinded pharmacist preparing the vaccines, so that vaccine or placebo doses can be prepared for each subject as appropriate. A designated unblinded statistician will be responsible for the computer generated randomisation schedule. Sealed copies of the randomisation code will be stored in a secure place. Following database lock, on receipt of authorisation from the Sponsor, a copy of the randomisation code list will be sent to the Study Statistician to conduct study unblinding.
 
Part B
 
Assuming significant efficacy of at least one dose of FLU-v against placebo is demonstrated in Part A, Part B will be conducted and test the optimal FLU-v dose from Part A (in terms of efficacy and safety) versus a current standard of care seasonal influenza vaccine. Details of Part B randomisation and blinding will be determined and documented in a future protocol amendment following the availability of the unblinded key efficacy and safety results from Part A. Approval will be sought via a substantial amendment from the competent authority before part B can commence.

CHALLENGE VIRUS	Live, recombinantly derived A/CA/04/2009-like flu virus
CHALLENGE VIRUS ROUTE	Intranasal (both nostrils)
IMP SUPPLIER	PepTcell Limited (t/a SEEK)
IMP	FLU-v
IMP DOSE(S)	500 micrograms suspended in 0.5ml volume of water and adjuvant
PHARMACEUTICAL FORM	Lyophilised powder to be suspended for injection
IMP ROUTE	Subcutaneous Injection
CONTROL COMPOUND	Placebo (adjuvant Montanide ISA-51)
STUDY POPULATION	Healthy males and females aged 18 to 55 years of age
REPLACEMENT POLICY	Subjects will not be replaced post-influenza challenge on Day 0
PRIMARY OBJECTIVE	To determine the effect of FLU-v on reducing the incidence of Mild to Moderate Influenza Disease (MMID) defined as detectable viral shedding plus at least one symptom of influenza

SYNOPSIS	
PRIMARY ENDPOINT	Incidence of MMID
SECONDARY OBJECTIVES	To determine the overall effect of FLU-v on measurements of disease severity
SECONDARY ENDPOINTS	
• Viral shedding duration• Viral shedding quantitation• Symptom duration• Total number of symptoms experienced• Symptom severity score as measured by FLU-PRO Symptom Questionnaire• Incidence of vaccine related adverse events (diary card for 21 days after each vaccine)
EXPLORATORY OBJECTIVES	To explore the immunological responses to FLU-v
EXPLORATORY ENDPOINTS	
• Immunogenicity of FLU-v as measured by
◦ B-cell and T-cell responses to FLU-v both after vaccination as well as influenza challenge◦ Immunophenotyping• Broadness of protection as measured by culturing PBMCs pre-influenza virus inoculation in study with PBMCs (same subject) infected with influenza and assess killing of infected cells by PBMCs from vaccinated subjects and use sera containing non-neutralising antibodies and test killing of human influenza infected cells by complement activation or ADCC assays
SAFETY OBJECTIVES	To determine the safety and tolerability of FLU-v after vaccination in healthy subjects subsequently challenged with Influenza A 2009 H1N1 human challenge virus
SAFETY ENDPOINTS	
• Incidence of treatment-emergent AEs (TEAE), severity, seriousness and causality• Absolute values and change from baseline in routine clinical and laboratory parameters• Vaccine related physical examination findings• Concomitant medications
STUDY DESIGN	
• Study-specific screening (SSS) within 90 days prior to challenge• Vaccination on Day - 43• Vaccination on Day - 22

SYNOPSIS	
	
• Entry to quarantine on Day -2 or Day -1• Challenge Virus inoculation on Day 0• Subjects will be resident in the Quarantine Unit for a total of approximately 10 days (from Day -2 or Day -1 to Day 7)• End of quarantine phase is achieved on Day 7 or until two negative diagnostic tests for influenza on two separate but consecutive days and are otherwise clinically stable.• Follow-up visits: Day 35 (+/- 3) and Day 63 (+/- 5) days.
PROCEDURES AND ASSESSMENTS	
During the study the following assessments and procedures will be performed:
 
• Written informed consent• Eligibility criteria• Height, body weight, body mass index (BMI),• Medical history• Demographics• Prior medications• Randomisation Dosing with FLU-v-004 or placebo• Challenge Virus inoculation• Complete physical examination• Directed physical examination• Vital signs (blood pressure [BP], respiratory rate [RR], heart rate [HR], peripheral arterial oxygen saturation [SpO₂])• Tympanic temperature• 12-lead ECG• Spirometry• FLU-PRO Symptom Questionnaire• Bloods:
○ Challenge Virus serology○ Haematology○ Biochemistry○ Cardiac enzymes○ Hepatitis A, B and C and human immunodeficiency virus (HIV) serology○ Serum follicle stimulating hormone (FSH) (post-menopausal females)○ Beta-human chorionic gonadotropin (β-hCG) pregnancy test (females).○ Whole and serum blood collection for immune response analysis• Nasopharyngeal swab
○ Respiratory virus screen○ Viral load (TCID₅₀ and/or RT-qPCR).

SYNOPSIS	
	
• Breath alcohol test• Urine:
◦ Urinalysis (dipstick)◦ Pregnancy test◦ Drugs of abuse.• Adverse events• Concomitant medications
END OF STUDY	The last subject's last scheduled visit (LSLV).
EXPECTED DURATION OF SUBJECT PARTICIPATION	Approximately 153 days or 22 weeks from screening to LSLV
OVERALL DURATION OF CLINICAL PHASE	Approximately 18 months
STATISTICS	
The hypothesis is that vaccination with 1 dose or two doses of FLU-v + adjuvant will significantly reduce MMID when compared to individuals vaccinated with placebo.
 
The primary objective of this study is to examine whether there is a difference in the MMID post inoculation rates between either of the 2 FLU-v arms and placebo. A sample size of 41 subjects per arm (total 123) will provide 80% power to detect a difference in MMID rates of 0.70 versus 0.40 (ie difference of 0.30) using a one sided 0.05 significance level.
 
In this study, the main comparisons are for each of the FLU-v dose groups to placebo. The study will also compare the two FLU-v dosing arms but the study will not have adequate power to detect a significant difference in MMID rates at the predicted treatment rates. This study does not control for multiple comparisons since we are trying to maintain a small sample size but have high power to detect the predefined primary objective of efficacy versus placebo when FLU-v is truly beneficial. All comparisons will be made at the one sided 0.05 significance level.
 
FLU-v Statistical Analysis Plan
 
MMID rates in the 2 FLU-v groups and placebo group will be compared using a Fishers exact test. 95% confidence intervals around the difference in rates between the FLU-v groups will be presented. Adverse event rates between groups will also be compared using Fishers exact test. The secondary endpoints will be examined by calculating the median and interquartile range

SYNOPSIS	
	and then performing a two-sided Wilcoxon Rank Sum Test at the 0.05 significance level.
STOPPING CRITERIA	
The study will be terminated if:
 
• One or more subjects experience a vaccine related SAE or two or more subjects experience severe or clinically significant AEs within same organ class and confirmed by repeat sample if considered to be at least possibly related to the FLU-v vaccine.• One or more subjects experience any severe clinically significant illness from influenza challenge.

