9.3.2 Virus Inoculation (Day 0)

All baseline procedures and tests will be performed prior to challenge virus administration. Once it has been determined that the participant still meets eligibility criteria for the study and that he/she is comfortable in the unit, administration of the challenge virus will proceed at a dose of 10^7 TCID₅₀ on Day 0. Once the influenza challenge virus has been administered, participants will remain hospitalized in isolation on the unit for a minimum of 8 additional days and will be discharged only after they meet the discharge criteria described below.

9.3.3 Day 1 through 7

While admitted to the Quarantine Unit, participants will remain in isolation in their room. Participants will undergo study procedures which will be conducted as detailed on the Time and Events table 9.2

Participants will be discharged when they meet the following discharge criteria: 2 consecutive negative morning nasal swabs (that occur on 2 different but consecutive days) for influenza A, are afebrile, show no signs of significant influenza symptoms, and are clinically and hemodynamically stable. It is expected that participants will shed virus for 3 to 5 days post inoculation; therefore, we expect most participants to have 2 consecutive negative nasopharyngeal swabs by Day 7 of the study.

The FLU-PRO questionnaires will be completed in paper form.

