A randomized, double-blind, placebo-controlled efficacy and safety trial of FLU-v administered as 2 vaccinations or 1 vaccination vs placebo prior to intranasal challenge with the Influenza A 2009 H1N1 human virus.

In this study, the main efficacy comparisons are for each of the FLU-v groups to placebo. The study will not compare the two FLU-v dosing arms as the study may not have enough power to detect a significant difference in the primary efficacy endpoint of mild to moderate influenza induced disease (MMID) rates between the FLU-v groups.

2 Current Approved Study Protocol

The current approved study protocol is version 3.0 dated 18APR2017.

3 Study Hypothesis

The hypothesis is that vaccination with one dose or two doses of FLU-v + adjuvant will significantly reduce MMID when compared to individuals vaccinated with placebo.

4 Sample Size Justification and Analysis Plan

Sample size was calculated for 3 groups, a placebo group and 2 Investigational Medicinal Product (IMP) (i.e. one dose and two doses of FLU-v) groups. Each FLU-v arm will be compared to the placebo arm. Groups are randomized 1:1:1. All comparisons are at the 0.05 one-sided alpha level, and any p-value less than 0.05 would be considered as significant. This may increase the type-I error rate of potentially moving forward with an inactive treatment, but is appropriate for an early phase II trial of this type. Sample sizes assuming two different placebo MMID rates and for 80% power are given in Table 1 below.

Table 1.

Probability (rate) of MMID		Sample size per arm	Total sample size	Power	One-sided alpha
Placebo	Vaccine				
0.7	0.4	40	120	80%	0.05
0.8	0.5	37	111	80%	0.05

Table 1 shows that a sample size of 120 (40 per group) provides good power (80%) for a placebo MMID rate of 0.7 and an absolute reduction of 30%. The difference is clinically meaningful and the assumptions of a placebo MMID rate of 0.70 is reasonable and based on past experience.¹

5 Analysis Plan and Reports

The primary analysis population will be the Intent to Treat (ITT) population and will be used for the analysis of all primary and secondary endpoints. The ITT will include those participants who received both vaccination and challenge with an influenza virus.

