 - If a subject has no nasal swab data on two consecutive days, and the available recorded data shows no shedding, the endpoint will be considered as missing. Similarly, if symptom data is not recorded on two consecutive days, and the available recorded data shows no symptoms, the endpoint will be considered as missing for that subject. However, if a subject is positive for viral shedding with the available recorded data, that subject will be included in the analysis. Similarly, if the subject shows at least one symptom within the recorded data, that subject will be included in the analysis.

- Modified MMID
 - Incidence of at least two symptoms (on PAI) and viral shedding (RT-qPCR) at any time during the quarantine from evening of Day 1 post-inoculation through Day 7. If a subject has no nasal swab data on two consecutive days, and the available recorded data shows no shedding, the Modified MMID will be considered as missing. Similarly, if symptom data is not recorded on two consecutive days and the available recorded data shows no symptoms this endpoint will be considered as missing for that subject. However, if a subject is positive for viral shedding and experiences at least two symptoms with the available recorded data, that subject will be included in the modified MMID analysis.
- Viral shedding duration (days)
 - Measured from the first day with a positive test on RT-qPCR, starting from evening of Day 1 post-inoculation until the last day with a positive test during the expected quarantine period (up to Day 7). Intervening negative or missing test days will be included in the duration. If no positive test occurs, duration is counted as zero.
- Viral shedding quantitation (RT-qPCR)

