 - Area under the curve (AUC) will be calculated based on each timepoint tested on RT-qPCR (log copy number/ml) record from evening of Day 1 post-inoculation to the morning of Day 7 (last timepoint before expected quarantine discharge) using Trapezoidal rule, and those samples below lower limit of quantification (LLOQ) will be replaced by half of LLOQ. Linear interpolation will be used for a single missing measurement. If more than one consecutive point is missing, the endpoint is considered as missing. RT-qPCR peak during entire quarantine period (i.e. the highest level of RT-qPCR recorded anytime during the quarantine period, starting from evening of Day 1 post-inoculation up to Day 7. A single maximum RT-qPCR (peak) will be identified for each subject during the quarantine on the assumption that a peak is recorded during the quarantine. Thus, there will not be imputation to predict the peak for subjects who have suspected missing peak data as it is implausible to predict the missing peak from the rest of the existing data.
- Symptom duration in days (PAI)
 - Number of days from first symptom noted, starting the evening of Day 1 post-inoculation until the day of last symptom noted up to Day 7. Intervening days with no symptoms or

missing symptom data will be included in the duration. If no symptoms occur during the entire period, number of days is zero.

- Total number of symptoms experienced (PAI)
 - Mean of total number of symptoms (upper and lower respiratory and systemic symptoms) experienced from the evening of Day 1 post-inoculation until the day of last symptom noted during the expected quarantine period (up to Day 7). Calculated as the total sum of symptoms experienced divided by the number of days in which symptoms were collected.
- Total symptoms score peak (PAI)
 - The highest level of the total sum of all upper and lower respiratory tract and systemic symptoms recorded on any day starting from the evening of Day 1 post-inoculation until the day of last symptom noted during the expected quarantine period (up to Day 7).
- Symptom severity score as measured by FLU-PRO Symptom Questionnaire
 - Mean of daily score over all study quarantine days from Day 1 post-inoculation to Day 7. If a day has missing data, this day will be excluded from the mean calculation (days with 0 as the symptom severity will be included in calculating the average).

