- Comparison of each treatment group to placebo of the proportion of asymptomatic infected subjects defined as subjects with symptom score of zero (PAI) from Day 1 post-inoculation time-point through the expected end of quarantine (Day 7) with at least one positive result for viral shedding (RT-qPCR) in any of the quarantine days from the evening of Day 1 post-inoculation.
- Summary of Adverse Events from the Post-Vaccination Diary Card
 - The number of subjects who self-reported at least once any of the adverse events listed in the Post-Vaccination Diary Card during the 21 days following first vaccination and 21 days following second vaccination. Data will be presented for each treatment group by event and according to severity (mild, moderate, severe). The number of subjects in each treatment group with no self-reported events will also be presented.

The statistical software to be used for the analyses will be SAS (version 9.4) and R (version 3.43). The analyses of the secondary binary endpoints will be performed by comparing the rates in each of the FLU-v groups to the placebo group using one-sided Fisher's exact test. For all secondary endpoints, the primary analysis will assume missing data is missing at random so missing data will be ignored.

The analysis of all continuous secondary endpoints will be performed by calculating the median and interquartile range and then performing a one-sided Wilcoxon Rank Sum Test at 0.05 level of significance. These data will be reported as tables and figures as described in sections 8-9 of this document.

Statistical analysis will be performed by a junior statistician at NIAID-NIH and will be reviewed by the senior statistician. In addition, the Senior Clinical and Scientific Leader, will repeat the statistical analysis to validate the results.

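### The continuous severity endpoints get arm medians and a Wilcoxon p-value but no between-arm estimate with a confidence interval, and with zeros scored the medians can hide the effect when attack rates are near or below one half

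*Protocol*

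**What the plan says.** The secondary objective in both documents is the effect of FLU-v on disease severity. The protocol synopsis says "The secondary endpoints will be examined by calculating the median and interquartile range". The Wilcoxon test that it adds is two-sided, at the 0.05 level; Protocol 16.4 and 16.6 repeat this. SAP 5.4 says "The analysis of all continuous secondary endpoints will be performed by calculating the median and interquartile range", followed by "performing a one-sided Wilcoxon Rank Sum Test at 0.05 level of significance". SAP section 8 adds box plots of medians and quartiles by arm. Neither text plans a between-arm estimate or a confidence interval for these endpoints. The table shells are a separate document and could not be read.

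The analysis set keeps subjects who never become infected (SAP section 5): "The ITT will include those participants who received both vaccination and challenge with an influenza virus". SAP 5.4 sets shedding duration as follows: "If no positive test occurs, duration is counted as zero". For symptom duration: "If no symptoms occur during the entire period, number of days is zero". For the viral load AUC, samples below the quantification limit are set to half that limit, which is a floor above zero.

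Protocol 9.3.3 gives the expected course: "It is expected that participants will shed virus for 3 to 5 days post inoculation". The power table in Protocol 16.2 has placebo MMID rates of 0.70, 0.60 and 0.50, and vaccine rates from 0.47 down to 0.21.

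**The concern.** A p-value says whether the arms differ. The severity objective also asks by how much, and the only quantities planned for that are the two arm medians and their quartiles. With a block of subjects at zero, an arm's median is zero whenever fewer than half of the arm sheds, however long the shedders shed. Two arms can then both report a median of zero days beside a significant test, leaving the reader with no size for the effect.

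Low attack rates are a real prospect. Protocol 5.2.3.1 records that the earlier FLU-v challenge study aimed for 70% to 80% on placebo and did not achieve it.

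**Working it through.** **Inputs.** 41 per arm and the MMID rates come from Protocol 16.2, the 3-5 days of shedding from Protocol 9.3.3, and the zero rule from SAP 5.4.

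**Assumptions not in the documents.** (a) The shedding rate equals the MMID rate. MMID needs shedding plus a symptom, so the true shedding rate is at least that high. (b) Shedders' durations are uniform on 3, 4, 5 days, or on 1 to 7 days as a sensitivity case, with the same distribution in both arms.

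**Step 1: reproduce the plan's power.** Exact power of the one-sided 0.05 Fisher test with 41 per arm is 0.813 at 0.70 v 0.40 (stated 0.80) and 0.819 at 0.50 v 0.21 (stated 0.81). The design figures are sound.

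**Step 2: when is an arm's median above zero?** With 41 subjects the median is the 21st ordered value, so it exceeds zero only if at least 21 shed: P(median > 0) = P(Bin(41, p) ≥ 21).

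| p | 0.70 | 0.60 | 0.50 | 0.47 | 0.40 | 0.30 | 0.21 |
|---|---|---|---|---|---|---|---|
| P(median > 0) | 0.996 | 0.903 | 0.500 | 0.349 | 0.097 | 0.004 | <0.001 |

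**Step 3: what the trial would display.** Both arms have mean duration 4 days among shedders, so the true difference in means is 4 × (p placebo − p FLU-v). At 0.70 v 0.40 that is 4 × 0.30 = 1.20 days; at 0.50 v 0.21, 4 × 0.29 = 1.16; at 0.90 v 0.70, 4 × 0.20 = 0.80. The results below come from 20,000 simulated trials per row, using the tie-corrected Wilcoxon test.

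| Shedding rates | Days if shedding | Mean difference | Medians 0 v 0 | Of these, one-sided p<0.05 | Median gap ≥3 days favouring FLU-v |
|---|---|---|---|---|---|
| 0.70 v 0.40 | 3-5 | 1.20 | 0.3% | – | 90% |
| 0.70 v 0.40 | 1-7 | 1.20 | 0.3% | – | 46% |
| 0.60 v 0.30 | 3-5 | 1.20 | 10% | 42% | 90% |
| 0.50 v 0.21 | 3-5 | 1.16 | 50% | 75% | 50% |
| 0.50 v 0.21 | 1-7 | 1.16 | 49% | 74% | 3% |
| 0.90 v 0.70 | 3-5 | 0.80 | 0% | – | 0.3% |
| 0.50 v 0.50 | 3-5 | 0 | 25% | 0.6% | 25% |
| 0.50 v 0.50 | 1-7 | 0 | 25% | 0.6% | 1.4% |

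A separate run put the share of significant 0 v 0 results at 0.50 v 0.21 at about 73%, so 73-75% is a fair range. With the protocol's two-sided test it is 61%.

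**Step 4: is the test damaged?** No. At 0.50 in both arms it rejects in 4.9% of trials one-sided and 4.7% two-sided. At 0.70 v 0.40 it rejects in 81% and 71%.

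**Step 5: how would the added estimates behave?** At 0.70 v 0.40 with 3-5 days the mean difference has standard error 0.44, and 95% of trials fall between 0.32 and 2.05 days. The Mann-Whitney probability that a FLU-v subject does better, counting ties as half, is 0.5 + (p placebo − p FLU-v)/2 when shedders' durations have the same distribution in both arms. That gives 0.65 at 0.70 v 0.40 and 0.645 at 0.50 v 0.21. A Hodges-Lehmann shift would not serve: ties at zero make it exactly 0 in 43% of trials at 0.70 v 0.40.

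**The case against.** The strongest reply is that this is a matter of presentation for secondary endpoints. The test is valid. The planned IQRs and box plots partly show the zeros: at 0.50 v 0.21 with 3-5 days the typical IQR is 0-4 on placebo and 0-0 on FLU-v. SAP 5.3 lists presence or absence of symptoms or shedding, Table 14.2.2.2 appears to cover those proportions, and MMID, modified MMID and asymptomatic infection are compared by arm. All of this stands and limits the point. None of it quantifies the difference in duration or severity.

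A reader might also infer that the median gap jumps between 0 and 3-4 days by chance and misstates a true effect of about 1 day. The documents do not support that as a general statement:

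- At the design rates of 0.70 v 0.40 with 3-5 days the gap is stable, at 3-4 days in 90% of trials. The population medians really are far apart. The mean difference of 1.2 days is another estimand, so the gap is not an error.
- Chance jumps of 3 days or more need a rate near 0.5 and durations confined to 3-5 days. Protocol 9.3.3 states that range only as an expectation, and SAP 5.4 allows other values. With 1-7 days, the spurious gap favouring FLU-v under no effect falls from 25% to 1.4%.
- A zero that follows directly from not being infected is exact only for shedding duration. Symptom and FLU-PRO scores can exceed zero without infection, and the viral load endpoints were not simulated.

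Finally, neither added estimate separates a lower attack rate from shorter illness. In every effect scenario above the mean difference is positive although no shedder's duration was shortened. That is correct, and the SAP should say so.

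**Conclusion.** The point holds as a gap in effect estimation; inference is unaffected. The texts plan no between-arm estimate or interval for the continuous severity endpoints, and the planned medians cannot reliably supply one when an arm's shedding rate is near or below 0.5. The clearest case is the protocol's own 0.50 v 0.21 row: half of trials would report 0 v 0 days, about three quarters of them with one-sided p<0.05, under either duration assumption. At 0.70 v 0.40 the medians answer a different question from the mean. At 0.90 v 0.70 the median is no longer governed by the zeros and the problem largely goes.

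These sizes rest on the shedding rate equalling the MMID rate and on the assumed durations. Higher shedding rates weaken the point. The table shells might already contain an estimate, but nothing in the SAP text commits to one.

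**What to change.** In SAP 5.4, keep the Wilcoxon test, and keep medians and IQRs as description. Add for each FLU-v arm v placebo:

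- the Mann-Whitney probability with 95% CI, which matches the test, for every continuous severity endpoint;
- for shedding duration and symptom duration, the difference in mean days over all challenged subjects with a bootstrap 95% CI.

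Present both beside the proportions shedding and symptomatic in Table 14.2.2.2. State that they combine attack rate and duration. Label any summary among shedders only as descriptive and non-randomised, since shedding occurs after vaccination and may depend on it.

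While this text is open, reconcile the sidedness of the Wilcoxon test: it is two-sided in the protocol and one-sided in SAP 5.4, while SAP section 6 declares no change to the protocol's analyses beyond the post-hoc ones.

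The cost is a few sentences in the SAP, extra table columns and a little more analysis work. No new data are needed.
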